#### Follow up Period

Follow-up visits will occur 4 and 8 weeks after EOT visit to allow for determination of immunogenicity and potential prolonged PD effects, and evaluation of safety. Participants will be discharged from follow-up 3 months after the last dose of study intervention.

The maximum amount of blood collected from each participant over the duration of the study, including any extra assessments that may be required, will not exceed 450 mL in 3 months. Repeat or unscheduled samples may be taken for safety reasons or for technical issues with the samples.

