Urinalysis	X	
Pregnancy test (female participant of childbearing potential only) f		X
CCI		
See CT scan collected as part of the s	afety assessments above	ve
Pandemic impact assessment	X	X

Echocardiogram and CT dates will be scheduled at SV1, to occur post-confirmation of eligibility at SV2.

May be performed on a separate day ahead of study visit if required. The analysis can either be performed locally or centrally.

Only required if a CT scan as part of SV2 is performed. If required must be done prior to CT scan.

AstraZeneca

AE = Adverse event; BD = Bronchodilator; CAT = COPD assessment test; COPD = Chronic obstructive pulmonary disorder; CT = Computed tomography; ECG = Electrocardiogram; ePRO = Electronic patient reported outcomes;  $FEV_1$  = Forced expiratory volume in 1 second; FSH = Follicle stimulating hormone; HIV = Human immunodeficiency disease; IGRA = Interferon gamma release assay; NT-proBNP = N-terminal pro-brain natriuretic peptide; PEF = Peak expiratory flow; SAE = Serious adverse event; SARS-CoV-2 = severe acute respiratory syndrome coronavirus 2; SGRQ = St George's Respiratory Questionnaire; SV = Study visit; TB = Tuberculosis.

Table 3 Schedule of Activities: Study Intervention and Follow-up

Study Period					Interver	ition Peri	od				Follo	ow-up		
Visit Number	SV3	SV4 TC	SV5	SV6	SV7	SV8	SV9	SV10	SV11	SV12	SV13	SV14		
Study Day (SV5 to SV14 window: ± 3 days)	1	2	15	29	57	85	113	141	169	197	225	253		
Study Week	0	0	2	4	8	12	16	20	24	28	32	36	E/D	E/A a
Efficacy assessments	•	•		ļ.		ļ.						•		
Clinic spirometry (pre-BD)	X		X	X	X	X	X	X	X	X	X	X	X	
Clinic spirometry (post-BD)						X	4		O *	X			X	
Airwave oscillometry	X					X	4			X			X	
Use of at home spirometry b and eDiary c		Every day throughout inter ention and follow-up periods												
Assess adherence to the completion of eDiary entries and home device use (including PEF)	X	X	X	X	X	х	X	X	X	X	X	X	X	X
Cough monitoring (24 hour monitoring post clinic visit)			D		) >	X								
CCI														
ePRO: SGRQ	X			X		X				X			X	
CCI													'	
Study Participant Feedback Questionnaire (Optional)	X					X						X	X	
Assessment of COPD exacerbations	X	X	X	X	X	X	X	X	X	X	X	X	X	X
Safety assessments		•		l.		l.							1	
Physical examination a, c	X		X	X	X	X	X	X	X	X	X	X	X	X
Weight	X					X				X			X	
ECG	X					X				X		X	X	
Vital signs d	X		X	X	X	X	X	X	X	X	X	X	X	

Table 3 Schedule of Activities: Study Intervention and Follow-up

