#### 4.2.3 Rationale for Intervention Period Duration

The last dose is administered at Week 24 and the end of treatment is 4 weeks later (Week 28).

Based on available data, the improvement in FEV1 assumed in the sample size determination (Section 9.2) is expected to be achieved by Week 12. However, improvement in FEV1 is considered important but not sufficient to meet the unmet medical need in COPD. To enable evaluation of the secondary endpoint of COPDCompEx, the treatment is continued after collection of primary endpoint data, to collect further events.

AstraZeneca

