# 7 DISCONTINUATION OF STUDY INTERVENTION AND PARTICIPANT DISCONTINUATION/WITHDRAWAL

# 7.1 Discontinuation of Study Intervention

The PI may determine it necessary on medical grounds for a participant to permanently discontinue (definitive discontinuation) study intervention. Note that discontinuation from study intervention is NOT the same thing as withdrawal from the study.

If study intervention is permanently discontinued, the participant will remain in the study and attend all remaining intervention period and follow-up period visits.

See the SoA (Section 1.3) for data to be collected at the time of discontinuation of study intervention and follow-up and for any further evaluations that need to be completed.

An individual participant will not receive any further study intervention if any of the following occur in the participant in question:

AstraZeneca

- 1 Withdrawal of consent to further treatment with study intervention.
- 2 Lost to follow-up.
- 3 Any anaphylactic reaction to study intervention requiring epinephrine administration.
- 4 Any treatment-emergent AE that is Grade  $\geq 4$  in severity (see Appendix B).
- 5 Any treatment-emergent SAE that is in the cardiac disorders system organ class, except atrial arrhythmias.
- Confirmed diagnosis of new onset of heart failure during the study (except for transient heart failure secondary to atrial arrhythmia). For a participant with suspected new onset of heart failure, the participant should not be administered study intervention unless and until the diagnosis is refuted. Study intervention should also be temporarily withheld during any episode of transient heart failure secondary to atrial arrhythmia.
- Any other AE that, in the opinion of the investigator or the sponsor, warrants discontinuation of further dosing of study intervention.
- 8 Pregnancy.
- 9 Following randomization, the participant mee\* > 1 the exclusion criteria or fails to meet all of the inclusion criteria for study par cipe tion.
- 10 Any AECOPD with duration > 14 days.
- 11 The participant misses 2 consecutive doces.

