#### Table 17Analysis visit windows for cough monitoring

Protocol Visit	Week	Analysis Visit	Scheduled Study Day	Visit Window for Analysis (Days)
SV2	Week -3 to -1	Baseline	1	All assessments prior to the first administration of investigational product
SV8	Week 12	Visit 8, Week 12	85	≥2

SV = Study Visit.

Any data collected at early discontinuation and unscheduled visits will be listed and will be included in the definition of maximum/minimum value. The Early Discontinuation and Unscheduled visits will be included when applying the visit windows to ensure that all available data are used in the analysis.

Daily CCI E-RS: COPD, BCSS, cough VAS etc.) will primarily be summarised and analysed as 4-weekly averages, separately. The assessment period of visit windows will be defined in Table 18.

Table 18Labelling of 4-we	eekly periods for CCI and eDiary variables
4-weekly period	Label
Baseline: as defined in Section 3.1.1	Evening of Day -14 to Morning of Day 1 (Baseline)
Period 1: Evening of Day 1 – Morning of	Day 29 Day 1 – 29 (Week 4)
Period 2: Evening of Day 29 – Morning o	f Day 57 Day 29 – 57 (Week 8)
Period 3: Evening of Day 57 – Morning o	f Day 85 Day 57 – 85 (Week 12)
Period 4: Evening of Day 85 – Morning o	f Day 113 Day 85 – 113 (Week 16)
Period 5: Evening of Day 113 – Morning	of Day 141 Day 113 – 141 (Week 20)

#### CONFIDENTIAL AND PROPRIETARY 33 of 167

JCI

4-weekly period	Label
Period 6: Evening of Day 141 – Morning of Day 169	Day 141 – 169 (Week 24)
Period 7: Evening of Day 169 – Morning of Day 197	Day 169 – 197 (Week 28)
Period 8: Evening of Day 197 – Morning of Day 225	Day 197 – 225 (Week 32)
Period 9: Evening of Day 225 – Morning of Day 253	Day 225 – 253 (Week 36)

For all other assessments, there will be no analysis visit windows, the data will be reported according to CRF visit.

For variables analysed using a 4-weekly period, all the days should be considered.

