#### End of Treatment analysis

The End of Treatment analysis will occur once all participants have either completed the Week 28 assessments or withdrawn from the study. This will include all available data from all visits up to and including Week 28, irrespective of whether the participant discontinued study intervention or received reliever therapy. The statistical analysis will compare CCI of MEDI3506 to Placebo.

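### Protocol Section 4.1 ends follow-up 3 months after the last dose without exception, contradicting Section 7.1 for early stoppers; followed literally, it drops SV12 (Week 28) for any last dose at or before Week 12

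*Protocol*

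**What the plan says.** Protocol Section 4.1, under Follow up Period, first places the follow-up visits relative to the end-of-treatment visit ("Follow-up visits will occur 4 and 8 weeks after EOT visit"). It then gives a discharge rule: "Participants will be discharged from follow-up 3 months after the last dose of study intervention". That rule is tied to each participant's own last dose and carries no qualification.

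Protocol Section 7.1 covers early stopping: "If study intervention is permanently discontinued, the participant will remain in the study and attend all remaining intervention period and follow-up period visits". It does not name SV14, but SV14 (Week 36, Day 253) is the last follow-up visit in Table 3.

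The SAP is written for retention after stopping:

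- Of the End of Treatment analysis, Section 4 says "This will include all available data from all visits up to and including Week 28, irrespective of whether the participant discontinued study intervention".
- Section 4.2.1 counts, at each scheduled visit, participants who are off treatment but still in the study.
- Section 4.2.4.5 repeats the FEV1 repeated-measures model with data to Week 36.

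No text in either document limits the 4.1 sentence to completers or says which section prevails.

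**The concern.** For anyone who stops study intervention early, Sections 4.1 and 7.1 give different end dates. A site working from 4.1 could discharge such a participant months before SV14.

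The data at risk are those after discontinuation, which the analyses through Week 28 and Week 36 are meant to include. SAP Sections 3.1.4 and 4.1.2 impute no missing efficacy values, so the model would have to stand in for observations that were never collected. The reasons for stopping in Section 7.1 include adverse events of Grade 4 or higher, serious cardiac events, exacerbations longer than 14 days and two consecutive missed doses. They also include consent withdrawal, loss to follow-up and pregnancy. Missingness related to outcome is therefore plausible, though not certain. Where 4.1 was applied, the Week 28 results would drift from an all-data comparison towards an on-treatment one, and the length of safety follow-up would differ between sites.

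**Working it through.** **Inputs.** Protocol Table 3 gives dose days 1, 29, 57, 85, 113, 141 and 169 (Weeks 0 to 24). It gives visit days SV8 = 85, SV9 = 113, SV10 = 141, SV11 = 169, SV12 = 197, SV13 = 225 and SV14 = 253, each ± 3 days. SAP Table 7 sets the Week 28 window for pre-bronchodilator clinic spirometry at Days 184 to 211. The protocol does not define 3 months in days, so I take 84 days (12 weeks) to 92 days (the longest three calendar months).

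**The plan's own figure.** For a participant who receives all doses, SV14 minus last dose = 253 − 169 = 84 days = 12 weeks, or 84/30.4375 = 2.76 months. The 4.1 sentence is thus a fair rounding for completers.

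**Discharge day under 4.1 = last dose day + 84 to 92.**

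| Last dose | Dose day | Discharge day | Scheduled visits after discharge |
|---|---|---|---|
| Week 0 | 1 | 85–93 | SV9 to SV14 |
| Week 4 | 29 | 113–121 | SV10 to SV14 |
| Week 8 | 57 | 141–149 | SV11 to SV14 |
| Week 12 | 85 | 169–177 | SV12 to SV14 |
| Week 16 | 113 | 197–205 | SV13, SV14 |
| Week 20 | 141 | 225–233 | SV14 |
| Week 24 | 169 | 253–261 | none |

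Under Section 7.1 the last column is empty in every row.

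**Is the Week 12 cut-off robust?** The latest discharge after a Week 12 dose is 85 + 92 = Day 177. That precedes the earliest SV12 day (197 − 3 = 194) and the SAP window (184). If the dose is given at the end of its ordinary window, 85 + 3 + 92 = Day 180, still before both. If it is delayed by the full 14 days that Section 4.1.2 allows for pandemic reasons, it falls on Day 99, and discharge falls on Days 183 to 191. That can touch the SAP window but is still before SV12. A Week 16 dose keeps SV12, though under the 84-day reading discharge falls on the day of SV12 itself (113 + 84 = 197).

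**Primary endpoint.** The earliest discharge follows a single dose: 1 + 84 = Day 85, the nominal day of SV8. With calendar months (89 to 92 days) it is Days 90 to 93, after the SV8 window closes on Day 88. Only the 84-day reading is tight.

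**COPDCompEx.** SAP Section 3.3.4 counts only events up to 28 days after the last dose, and Section 3.3.4.1 censors no later than that. Discharge at 84 days or more comes at least 84 − 28 = 56 days afterwards.

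**Other Week 28 measures.** SAP Tables 11, 12 and 16 open the Week 28 window at Day 142 for SGRQ, airwave oscillometry and post-bronchodilator spirometry. The SAP adds that "The Early Discontinuation and Unscheduled visits will be included when applying the visit windows to ensure that all available data are used in the analysis". A discontinuation or unscheduled value from Day 142 on could therefore be labelled Week 28, up to 197 − 142 = 55 days before the scheduled visit.

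**The case against.** The strongest reply is that no site should follow 4.1 this way. Section 7.1 is the specific rule for permanent discontinuation and says that stopping is not withdrawal. Section 4.1 itself requires all Table 3 assessments during the intervention period, and Section 8 makes adherence to the schedule mandatory. Sections 7.2 and 7.3 provide for leaving only by withdrawal or loss to follow-up. The sentence just before the discharge rule ties follow-up to the end-of-treatment visit, which is fixed at Week 28, so the rule reads most naturally as a description of completers.

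Much of this stands. A reader might infer that the protocol offers two equally valid rules; it does not, and retention is the better reading. But the 4.1 sentence sits under the heading where site staff would look for the end of follow-up, it is worded as an instruction, and nothing limits it.

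Two other stronger readings also fail. A reader might infer that all Week 28 data are lost for these participants; the Day 142 windows mean that some SGRQ, oscillometry and post-bronchodilator values could still be used. A reader might also infer that the exacerbation endpoint shifts towards on-treatment; for COPDCompEx the SAP already makes it on-treatment. Other exacerbation endpoints are redacted and cannot be judged.

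**Conclusion.** The contradiction is real and is in the current text, but its reach is limited. If a site applies 4.1 literally, SV12 is lost for a last dose at Weeks 0, 4, 8 or 12 under every reading of 3 months from 84 to 92 days. SV13 and SV14 are lost for a last dose at Week 16, and SV14 for Week 20. What clearly goes is the SV12 visit, pre-bronchodilator FEV1 and FVC at Week 28 with the emphysema objective that uses them, FEV1 to Week 36, and late safety follow-up. The primary comparison does not depend on it, apart from the tight 84-day case after a single dose.

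A reader might want a head count. For instance, 10% of 144 stopping early, spread evenly over the six earlier dose times, would give 144 × 0.10 × 4/6 = 9.6 participants. The documents do not support such a figure: they state no stopping rate and no distribution of stopping times. It would also require every site to prefer 4.1, and it counts people lost to follow-up or withdrawn, whose data would be missing under either text. The number affected cannot be computed. This is a wording conflict that should be corrected; it does not threaten the primary result.

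**What to change.** Reconcile Section 4.1 with Section 7.1. One way is to limit the 4.1 discharge sentence to participants who receive all 7 doses and to refer to Section 7.1 for those who stop study intervention early. Sections 7.2 and 7.3 should continue to govern participants who withdraw from the study or are lost to follow-up, so the new wording should not promise SV14 for everyone.

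The cost is one sentence in the protocol and a note to sites. It adds no visit beyond those that Section 7.1 already requires, changes no dosing or stopping criterion, and needs no change to the SAP.

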#### **Additional Visits**

A clinical assessment of any potential exacerbatic during the intervention and follow up periods will occur either at the next scheduled visit or, if necessary, an additional E/A visit prior to the next scheduled visit (see the SoA in Section 1.3).

For any participants with suspected here to rilure during participation in the study, an ad hoc echocardiogram and NT-proBNP measurements are required. In addition, for these participants, vital signs, physical examinations and any other examinations (eg, chest X-ray) can be performed at the investigato. 's discretion, following local standard practice.

# 4.1.1 Study (and Sub-Naudy) Conduct and Planned Mitigations During COVID-17 Pandems

Coronavirus disease 2019 has emerged as a worldwide pandemic disease with significant implications for public health. AstraZeneca accepts that a careful risk-benefit analysis should be performed in each region before initiating clinical research that impacts the clinical resources needed for the COVID-19 pandemic. Hence, AstraZeneca will monitor countries and sites, and the study will not begin until local and national governments and clinical sites have indicated that it is acceptable to conduct clinical studies, any stay-in-place or lockdown orders have been lifted, and the safety of site staff and participants can be ensured. Furthermore, each study site must have appropriate measures to ensure safety of site staff and participants.

It is recognised that depending on the location and facilities of a clinical site, study visit attendance may place participants at risk of exposure to SARS-CoV-2. Where visits need to occur at locations other than the primary study site (eg, CT scans or echocardiograms), then

AstraZeneca

the investigator should select appropriate locations given the current environment. It is accepted that additional visits (eg, as part of participation) necessarily entail an additional risk of exposure to SARS-CoV-2.

Furthermore, it is recognised that more general population-level measures to reduce infection rates (eg, travel restrictions) may inhibit the ability of participants to attend study visits. Necessary healthcare responses at sites to the pandemic (eg, additional infection control measures) may also inhibit the ability of a clinical site to effectively and properly conduct the study. Study visit attendance for dosing and for clinical assessments of treatment response are critical for the scientific value of the study.

Therefore, investigators should not enrol participants unless they have reasonable confidence that throughout the duration of the study:

- Participants will be able to attend study visits, w. ist avoiding contact with concentrations of COVID-19 patients (eg, hospital entrances used by such patients); and
- The site will be able to conduct the study effectively and safely, considering relevant national and local factors.

The primary endpoint will be analyzed using a real eated measures mixed effect model which, in the event of missing data, uses all data the are available.

AstraZeneca will routinely conduct risk-based enrolment assessments on a country and site level during the pandemic phase of COV. 7-19, and study monitoring will include:

- AEs associated with new creet 5. RS-CoV-2 infection
- Participants withdrawn d. to COV1D-19 illness
- Missed visits due ( COVID-1) related issues
- Other missing data.

It is accepted due to age, disease under study and common comorbidities the target population has risk-factors for severe COVID-19 illness. The ability to exclude the most at-risk patients whilst maintaining the target population and the relevance of the study is necessarily limited.

AstraZeneca

COPD may be a risk-factor for severe COVID-19 illness, and the following participants will not be included in the study (see Exclusion Criteria 1 and 2, Section 5.2):

- 1 Participants with active COVID-19 infection at screening.
- 2 Participants with a history of significant COVID-19 illness within 6 months of enrolment defined as:
  - (a) A diagnosis of COVID-19 pneumonia based on radiological assessment.
  - (b) A diagnosis of COVID-19 with significant new findings from pulmonary imaging tests.
  - (c) A diagnosis of COVID-19 requiring hospitalisation and/or oxygen supplementation therapy.

Because the screening/run-in period is at least 4 weeks, participants will be tested for active SARS CoV-2 infection using a nucleic acid test target. \( \text{g} \) SARS-CoV-2 at both screening visits (see SoA [Table 2]), and those with a positive result the either screening visit will become screen failures. This test may be performed either that a local laboratory or at the central laboratory.

Participants suspected of having contracted Co. "D-19 should be managed according to local and national guidelines to prevent spread of COVID-19 infection to staff and patients. These participants, as well as any who test pooit. The for SARS-CoV-2, should not be automatically discontinued from investigational product or be withdrawn from the study. Investigators should refer to Section 7 when considering participant discontinuation or withdrawal decisions. Sites will be required to provide documentation of a COVID-19 screening and mitigation plan that describes how and value participants would be tested if they are suspected to have SARS-CoV-2 infection. The plans should also describe mitigation activities designed to protect site was a others at the site, including other participants and patients. Appendix J contains an example screening questionnaire that may be used prior to each visit to identify participants with symptoms of, or recent risk factors for, SARS-CoV-2 infection.

Infection control measures should be followed in accordance with local and national guidelines including, but not limited to, staff screening and use of personal protective equipment.

# 4.2 Scientific Rationale for Singly Design

Chronic obstructive pulmonary disease \(\sigma\) heterogeneous disease (Segal and Martinez 2018) and as such any proposed treatment should be targeted at the participants within that diagnosis most likely to respond, and wit' to generatest unmet burden of disease. Chronic obstructive pulmonary disease is charact. 'zed by airflow limitation (post-BD FEV1/FVC < 0.70) that is not fully reversible, usually progressive and associated with an enhanced chronic inflammatory response in the lung. The Evaluation of COPD Longitudinally to Identify Surrogate Endpoints (ECLIPSE) observational study of 2163 participants with moderate-to-severe COPD found a mean rate of decline of FEV1 of 33 mL/year over 3 years, with higher rates of FEV1 decline in the presence of current smoking, emphysema, and BD reversibility (Vestbo et al 2011). Research on the impact of chronic bronchitis in COPD patients on mortality and FEV1 decline in a population-based cohort, showed that COPD participants with chronic bronchitis (n = 172) had a greater FEV1 decline (-38 mL/year, 95%) CI -61.7 to -14.6; p = 0.024) compared with COPD participants without chronic bronchitis, and also a higher risk of respiratory mortality (hazard ratio 2.16, 95% CI 1.12 to 4.17; p = 0.002) and increased risk of acute exacerbations (objective response 4.0, 95% CI 2.7 to 5.9; p < 0.001) (Lahousse et al 2017). However, emerging evidence (Dunican et al 2021; Kim et al 2021) demonstrates mucus hypersecretion at all stages of COPD, evident on CT imaging alongside even very extensive emphysema. This accumulation of mucus in the small airways can occur in the absence of significant symptoms (Hogg et al 2007), likely as a result

AstraZeneca

of the lack of cough receptors in the peripheral airways (Burgel and Nadel 2008). Patients with recurrent exacerbations have higher sputum inflammatory markers (Bhowmik et al 2000) which suggests that underlying inflammation may lead to disease progression, but yet may still contribute to the ongoing inflammation associated with disease progression (Anzueto 2010; Crooks et al 2000).

Patients with COPD and mucus hypersecretion therefore present a high unmet need. Current therapy for these patients consists of dual (ICS + LABA or LABA + LAMA) or triple therapies (ICS + LABA + LAMA), with add-on in the event of increased exacerbation history of such treatments as PDE4 inhibitors, and chronic macrolide (such as azithromycin) treatment. These add-on treatments, however, have issues associated with individual tolerability and antibiotic resistance which have hampered their use.

As discussed in Section 2.2, MEDI3506 mode of action is hypothesized to impact airway inflammation, mucus and cough symptoms, and lung Inction endpoints in COPD, and through modification of these factors, reduce frequency and severity of exacerbations.

This study tests the hypothesis that MEDI3506 will improve lung function in participants with COPD and chronic bronchitis, using FEV1 as the primary outcome measure. The study uses secondary outcomes to gather evidence to support the mode of action of MEDI3506, concentrating on lung physiology, mucus, cough, and ePROs related to symptoms and disease impact.

There will be one sub-study in this 'rial:

CCI

